### Intervention

Participants will self-administer light daily using a Litebook® (The Litebook Company Ltd.). The

	Protocol Name:	Management of post-TBI fatigue with light exposure
	Principal Investigator:	[name]., ABPP/Cn
	Primary Contact Name/Contact Info:	[name], [contact] , [name]
	Date Revised:	3/9/2016
	Study Number:	IF1813452

Litebook is a small (6" x 5" x 1") and lightweight (8 oz.) box. Users are instructed to place it about 18" from their face and within 45° of the visual field for 30 minutes within half an hour of waking each morning, for 4 weeks. The participant may eat, read, watch TV, etc. while sitting in front of the box. The Litebook utilizes light-emitting diodes (LED) to provide a full spectrum that mimics the visible spectrum of sunlight. Although they are white lights, they are blue light "enriched", peaking at 460nm in the blue spectrum, allowing recipients to experience benefits of larger doses of blue light than are present in normal white light, as well as potential benefits of full-spectrum light exposure. Ultraviolet light is filtered out to prevent retinal damage. A device that appears identical but that uses red LEDs emitting DRL, peaking between 625 and 650nm, will be used for the comparison group. Prior to randomization a member of the research team will train participants to use the light box and instruct them to call the research team if they have questions about its use.

**Study Monitoring and Safety**

Bright light therapy has an excellent safety profile and has been shown to be well tolerated by most patients. Side effects are infrequent; the most common ones are mild headache, eyestrain, nausea and agitation. Side effects generally remit spontaneously. Study exclusion criteria were chosen to maximize safety. We will ask subjects to inform us of any new or intensified symptoms or health problems that they experience while using the light box. If significant adverse effects are experienced, the participant will be directed to discontinue treatment temporarily and consult their physician. Subjects will be withdrawn from the study if they experience any clinically significant side effects beyond those anticipated or if side effects are severe. We will ask participants not to alter medication use during the study unless it is medically necessary, and to notify the research team if alterations are made.

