*Treatment effects.* Change scores were used for between-group comparisons to remove effects of any baseline differences between groups. Robust effect sizes in Cohen’s “medium” and “large” ranges were seen for BWL both between and within groups (0.32-1.56) on fatigue measures (see Appendix VI for all effect sizes). In most cases, effects were somewhat decreased at follow up but were generally in the medium range. This is unexpected, as past research indicates that treatment effects dissipate after treatment is discontinued. Medium or larger effect sizes were also noted for BWL on measures of daytime sleepiness, sleep quality and mood. Effect sizes for DRL were generally small.

Actigraphy findings indicated improvements in sleep in both groups but with larger effect sizes for BWL. Circadian rhythm data were more ambiguous, with modest changes in phase and rhythmicity in both groups. These findings suggest that BWL and DRL therapy are safe, feasible and credible for use with individuals with TBI, that the measures selected were sensitive to treatment effects and that BWL may be a promising treatment for PTBIF, with potential benefits for daytime sleepiness, mood, circadian rhythms and sleep as well. Indeed, daytime sleepiness, mood, circadian rhythms, and sleep quality may actually function as mediators or moderators of BWL treatment effects on PTBIF, given their documented responsiveness to light exposure. Because of the promising initial findings in our small pilot study and the need for empirically validated PTBIF treatment, an *Intervention Efficacy* trial investigating the effect of BWL on PTBIF is warranted. Based on: 1] the literature on alerting effects and cognitive benefits of BWL and the connection between PTBIF and cognition; 2] our own unpublished research suggesting the important role of anxiety in PTBIF and sleep disturbance; and 3] potential improvements in life satisfaction resulting from BWL effects on function, we will evaluate cognition, anxiety and life satisfaction as potential secondary effects of treatment.

To date, no trials of BWL treatment have been conducted in individuals with TBI. However,

	Protocol Name:	Management of post-TBI fatigue with light exposure
	Principal Investigator:	[name]., ABPP/Cn
	Primary Contact Name/Contact Info:	[name], [contact] , [name]
	Date Revised:	3/9/2016
	Study Number:	IF1813452

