**b) Study Timelines**

Subjects' participation in the study will last approximately two months. Assessments will be conducted at three points: T1 (baseline), T2 (end-of-treatment) and T3 (follow-up at one month post treatment). Actigraph data will be collected for 3 days at T1 (prior to the initiation of treatment). Participants will use the light box for 4 weeks and then return at T2 for repeat administration of the measures and Actigraphy for 3 more days. T3 will take place 4 weeks after light box treatment is completed and will not involve the Actigraph.

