**g) Provisions to Monitor the Data to Ensure the Safety of Subjects**

**Part I: Elements of a Data and Safety Monitoring Plan**

**MSSM Principal Monitor:**

The principal monitor will be the PI

Last Name: [name]

First Name: [name]

Academic Title: Jack Nash Professor, Vice Chair

	Protocol Name:	Management of post-TBI fatigue with light exposure
	Principal Investigator:	[name]., ABPP/Cn
	Primary Contact Name/Contact Info:	[name], [contact] , [name]
	Date Revised:	3/9/2016
	Study Number:	IF1813452

Department: Rehabilitation Medicine  
Mailing Address: [name]  
[name]

[contact]  
[contact]  
E-mail: [[contact]](mailto:[contact])

Bright light therapy has an excellent safety profile and has been shown to be well tolerated by most patients. Most of the risks of the intervention are relatively minor. Side effects are infrequent; the most common ones are mild headache, eyestrain, nausea and agitation. Side effects generally remit spontaneously. Study exclusion criteria (listed above) were chosen to maximize safety. Steps will be taken to exclude those at greater risk (e.g., individuals with depression, mania, chronic headache). Subjects will be asked to document any new or intensified symptoms or health problems that they experience while using the light box and to notify the research team of any. If significant adverse effects are experienced, the participant will be directed to discontinue treatment temporarily and consult their physician. Subjects will be withdrawn from the study if they experience any clinically significant side effects beyond those anticipated or if side effects are severe. Participants will be asked not to alter medication use during the study unless it is medically necessary to do so; they will be asked to notify the research team if they do so. Adverse events (including accumulated adverse events) will be monitored weekly by the PI (local monitor).

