**7) Risks to Subjects**

Bright light therapy has an excellent safety profile and has been shown to be well tolerated by most patients. Side effects are infrequent; the most common ones are mild headache,

	Protocol Name:	Management of post-TBI fatigue with light exposure
	Principal Investigator:	[name]., ABPP/Cn
	Primary Contact Name/Contact Info:	[name], [contact] , [name]
	Date Revised:	3/9/16
	Study Number:	IF1556212

eyestrain, nausea and agitation. Side effects generally remit spontaneously. Study exclusion criteria were chosen to maximize safety. Subjects entering the study are screened by the research coordinator using the Mini International Neuropsychiatric Interview (MINI) for any history of bipolar disorder or manic episodes. Those who endorse any past history of bipolar disorder or manic episodes are immediately disqualified from the study. Those who do qualify are contacted bi-weekly during the light therapy phase of the study to check in for any symptoms of mania, adverse events or other health concerns. Qualified subjects are also explicitly instructed to contact the PI and research team of any health problems they sustain while in the light treatment phase of the study. Other risks in the study are related to loss of private information and emotional discomfort or distress from personal questions asked during interviews and assessment screenings. These issues will be monitored for safety.

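### No adverse-event enquiry is described from T2 to T3 (4 of 8 post-randomisation weeks), and no T1 item is described for the four anticipated side effects

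*Combined protocol and SAP*

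**What the plan says.** **How events reach the study team.** Under Study Monitoring and Safety the rule is: "We will ask subjects to inform us of any new or intensified symptoms or health problems that they experience while using the light box". Section 8 (Provisions for Research Related Harm/Injury) repeats it. The monitoring plan in section g), Part I, has: "Subjects will be asked to document any new or intensified symptoms or health problems that they experience while using the light box". Section 7 (Risks to Subjects) adds staff-initiated contact, with participants "contacted bi-weekly during the light therapy phase of the study to check in for any symptoms of mania, adverse events or other health concerns", and asks them to tell the team about "any health problems they sustain while in the light treatment phase of the study".

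**How long participants are in the trial.** Study Timelines says "Subjects' participation in the study will last approximately two months": four weeks of light to T2, then four weeks to T3. Enrollment and Assessments asks participants not to use light between T2 and T3, and repeats the battery at both visits. No adverse-event question is named at either.

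**Oversight.** "Adverse events (including accumulated adverse events) will be monitored weekly by the PI (local monitor"). Part II has the PI monitor safety and requires adverse events to be reported to the ethics board and the sponsor. None of these provisions has an end date.

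**Anticipated effects and entry screening.** The effects named as most common are mild headache, eyestrain, nausea and agitation. Related exclusions cover chronic severe headache, light sensitivity, retinal disease, current major depression and bipolar or manic history. The statistical plan describes no adverse-event table.

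**The concern.** Each collection rule stops when the light stops, while the participant stays in the trial for as long again and is seen once more. A symptom that persists after T2, first appears after it, or follows the end of light would not be asked about.

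The plan itself treats these four weeks as a period in which outcomes may move. Of the pilot it says "In most cases, effects were somewhat decreased at follow up but were generally in the medium range", and it adds that earlier research had effects fading once treatment ends. Mania is singled out for active checking, but that checking also ends with the light phase.

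The second part is the reference point. Participants are asked for symptoms that are new or worse, but no T1 item is described for the four effects the plan expects. Milder headache, eyestrain, nausea or agitation can be present at entry, because the exclusions remove only the chronic severe form of headache and those sensitive to bright light. For these four effects, change would rest on the participant's recollection.

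At stake is the completeness and attribution of the safety information. The primary fatigue analysis is not affected.

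**Working it through.** **1. Schedule.** Inputs from Study Timelines: light for 4 weeks (28 days), T3 a further 4 weeks (28 days) later, preceded by 3 days of Actigraphy.

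- After light starts: 28 + 28 = 56 days = 8 weeks; 56/30.44 = 1.84 months.
- With the 3 baseline days: 59 days; 59/30.44 = 1.94 months.

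Both agree with the stated two months or so.

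**2. Coverage of scheduled time.**

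| Source | Participant enquiry or report | Period |
|---|---|---|
| Study Monitoring and Safety; section 8 | self-report | light-box use |
| Section g), Part I | participant documents symptoms | light-box use |
| Section 7 | bi-weekly staff contact; self-report | light phase |
| Section g), Part I | weekly PI review | no end date, but no participant contact |
| Section g), Part II | PI oversight and onward reporting | no end date, but no participant contact |

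Solicitation covers weeks 0 to 4. Uncovered share = 28/56 = 50%.

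**3. Coverage of person-time.** Inputs from Number of Subjects: 80 completers, 15% attrition, 95 enrolled. Reproduced: 80/(1 - 0.15) = 94.1, rounded up to 95. So 15 are expected to leave. The documents do not say when, so the timing is an assumption:

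- all at day 0: (80 x 4)/(80 x 8) = 320/640 = 50.0%
- all midway through treatment: 320/(640 + 15 x 2) = 320/670 = 47.8%
- all at T2: 320/(95 x 4 + 80 x 4) = 320/700 = 45.7%

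Losses after T2 move the share back towards 50%, so the range is about 46% to 50%.

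Participant-days without solicitation among planned completers: 80 x 28 = 2,240. Taking all 95 to T3 would give 95 x 28 = 2,660, but that ignores the plan's own attrition.

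**4. Baseline reference.** The outcomes listed under Endpoints are fatigue, sleepiness, circadian rhythms, mood, life satisfaction, cognition, anxiety and sleep quality. The battery is given at T1 and again at T2 and T3. None of the instruments named in the statistical plan is identified as recording headache, eyestrain, nausea or agitation. The psychiatric interview in section 7 is an entry screen and is not described as repeated for safety.

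**The case against.** The best defence is that an on-treatment window with prompted contacts is a reasonable choice for a low-risk home device. The plan says side effects are infrequent and generally remit without intervention. It reports none in the pilot, and it describes no delayed visual or manic effect. The uncovered weeks are also unexposed, so they should not be weighted like treatment days. This limits the seriousness of the gap, but it does not supply a question at T3.

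Several stronger readings are tempting and are not supported:

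- *The second month is unmonitored.* PI review and event reporting have no end date, so a volunteered event would be handled. Medication changes are to be notified throughout the study, and mood and anxiety are measured at T3. What is missing is enquiry.
- *Collection during treatment relies on participants noticing symptoms.* Section 7 provides staff contact that asks about them.
- *Symptoms starting in the last days of light have no collection point.* They start inside the stated window, and the participant then attends T2.
- *There is no baseline symptom record.* Several domains are measured at T1. The gap is confined to the four named effects, and even there the defensible statement is that no item is described: the battery is not itemised, and the content of the T2 user-experience questionnaire is not given.
- *The comparison of side effects between arms is unreliable.* No such comparison is planned, and randomisation balances pre-existing symptoms in expectation. A missing baseline costs precision and attribution; by itself it does not bias the arms.
- *Persisting fatigue benefit implies persisting harm.* The pilot statement concerns benefit only. It shows that the plan allows for change after treatment, and no more.

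**Conclusion.** The point holds in limited form. As written, adverse-event solicitation ends with the light-box phase, and none is described for 4 of the 8 post-randomisation weeks. That is about 46% to 50% of person-time, or 2,240 participant-days among planned completers, all of it off treatment. This follows from a stated rule, repeated across sections, and not from missing detail alone. Separately, no T1 reference is described for headache, eyestrain, nausea or agitation.

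The figures assume the planned 28 + 28 day schedule, 95 enrolled and 80 completing. The baseline statement assumes that no unlisted T1 instrument covers the four effects. The documents do not support saying that the period goes unmonitored, that change in symptoms cannot be judged at all, or that harm is expected after light stops. The change is worth making because it improves the safety information at small cost.

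**What to change.** 1. In Study Monitoring and Safety, section g) Part I, and sections 7 and 8, replace the limit to light-box use or the light phase with a window running from T1 to T3.
2. Use one short checklist in both arms: the four named effects, manic symptoms and one open question. Ask it at T1 (before randomisation), at the existing treatment-phase contacts, at T2 and at T3.
3. For any event still open at T2, record its status at T3.
4. Add to the statistical plan a descriptive table, by arm, of events new or worse than at T1, separately for T1 to T2 and T2 to T3.
5. If an existing T1 instrument already records any of the four effects, name it and drop the duplicate item.

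Cost: a few minutes at each visit or contact already planned, one form and one table. Prompted questions will give higher side-effect rates in both arms than spontaneous reports, so the results should not be set directly against rates collected spontaneously. No change to stopping rules or other clinical management is proposed.

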**e) Specimen Banking**

N/A

**f) Data Management and Confidentiality**

All data obtained from subjects will be treated confidentially. Only the principal investigators and research assistants will have access to information about subjects that is identifiable. Hard copy data at Mount Sinai and the Centre for Neuro Skills will be stored in a locked file cabinet in the research staff office, with identifying information stored separately. Hard copy data will not be transmitted between Mount Sinai and the Centre for Neuro Skills as it will not be necessary for analysis.

At Mount Sinai and the Centre for Neuro Skills, research data will be stored on secure networked drives with access limited to the research team and collected on secure, encrypted laptops. REDCap (Research Electronic Data Capture- a secure web-based data capture tool supported by Mount Sinai) will be used as a database management system for project data at Mount Sinai.

	Protocol Name:	Management of post-TBI fatigue with light exposure
	Principal Investigator:	[name]., ABPP/Cn
	Primary Contact Name/Contact Info:	[name], [contact] , [name]
	Date Revised:	3/9/2016
	Study Number:	IF1813452

REDCap is a secure web-based data capture tool developed by Vanderbilt University and supported by Mount Sinai's Research Information Technology Department. It ensures database designs meet institutional and sponsor standards for security and compatibility. Project data managed by REDCap will have research numbers only, no names or other identifying information. Since Mount Sinai is a partner institution of REDCap, project data will remain on Mount Sinai's secure servers and not be transmitted elsewhere by REDCap. All project data captured in REDCap will not have any identifiers other than the unique research identification numbers, and remain stored on Mount Sinai's secure servers.

Data collected through websites (Assessment Center for Neuro-QOL measures and CNS Vital Signs for cognitive assessment) will be stored securely on those sites without any identifiers other than the unique research identification numbers (see below). Medical records received will be stored in hard copy or scanned into encrypted files. Subjects will be given unique research identification numbers (codes) that will be used for analyses and reports. The link between identifying information and subjects' unique research codes will be stored in an encrypted file. The computer will be kept in a locked room in the research staff office. Access to the link will be limited to the principal investigator, the project coordinator, and the research assistants. Clinical information, if any, included in the research data is protected by the rules on medical record confidentiality of the Mount Sinai Medical Center and HIPAA. Identifying data will be kept separately to ensure participants' confidentiality. Data will be stored for the time period required by Mount Sinai regulations.

All visits completed remotely (via videoconferencing methods such as videochat or Skype) will be completed in a private room so that only the research team will be able to see and hear the research subject.

Data from the actigraphs and light boxes will be sent to [name] in a password protected, encrypted electronic database by [name], the project statistician or one of the research coordinators. All identifiers will be removed other than study ID numbers.

Data analyses are described in detail in the study protocol.

**g) Provisions to Monitor the Data to Ensure the Safety of Subjects**

**Part I: Elements of a Data and Safety Monitoring Plan**

**MSSM Principal Monitor:**

The principal monitor will be the PI

Last Name: [name]

First Name: [name]

Academic Title: Jack Nash Professor, Vice Chair

	Protocol Name:	Management of post-TBI fatigue with light exposure
	Principal Investigator:	[name]., ABPP/Cn
	Primary Contact Name/Contact Info:	[name], [contact] , [name]
	Date Revised:	3/9/2016
	Study Number:	IF1813452

Department: Rehabilitation Medicine  
Mailing Address: [name]  
[name]

[contact]  
[contact]  
E-mail: [[contact]](mailto:[contact])

Bright light therapy has an excellent safety profile and has been shown to be well tolerated by most patients. Most of the risks of the intervention are relatively minor. Side effects are infrequent; the most common ones are mild headache, eyestrain, nausea and agitation. Side effects generally remit spontaneously. Study exclusion criteria (listed above) were chosen to maximize safety. Steps will be taken to exclude those at greater risk (e.g., individuals with depression, mania, chronic headache). Subjects will be asked to document any new or intensified symptoms or health problems that they experience while using the light box and to notify the research team of any. If significant adverse effects are experienced, the participant will be directed to discontinue treatment temporarily and consult their physician. Subjects will be withdrawn from the study if they experience any clinically significant side effects beyond those anticipated or if side effects are severe. Participants will be asked not to alter medication use during the study unless it is medically necessary to do so; they will be asked to notify the research team if they do so. Adverse events (including accumulated adverse events) will be monitored weekly by the PI (local monitor).

**Part II. Data Monitoring Committee/Data Safety Monitoring Board (DMC/DSMB)**

The study’s safety will be monitored by the PI and PPHS in keeping with National Institute of Neurological Disorders and Stroke guidelines for monitoring clinical trials. He will monitor safety, adverse events, data quality, completeness and timeliness; compliance with goals for recruitment and retention; protocol violations; and scientific developments external to the study that may impact participant safety or the ethics of the study. All adverse events and safety issues will be reported to the PPHS and sponsor in concordance with Mount Sinai PPHS regulations.

**h) Withdrawal of Subjects**

Subjects may withdraw their participation at any time. We ask them to notify us in writing if they decide to withdraw. In addition, subjects will be withdrawn from the study if they experience any clinically significant side effects beyond those anticipated or if side effects are severe.

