**a) Number of Subjects**

To obtain the necessary sample size of 80 study completers with 40 in each treatment arm, we conservatively estimate that we will need to screen 136 individuals (30% negative screens) and enroll 95 of them (15% attrition).

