### Enrollment and Assessments

Potential participants who contact the research team and express interest in the study will undergo the informed consent procedure followed by a screening assessment to assess eligibility. We will obtain consent in accordance with federal and MSSM regulations. Participants who qualify for the study will complete the remaining items from the T1 battery at this point. To document the presence of TBI, they will be asked to provide detailed information about their injury (mechanism, date, severity) and provide medical records or sign releases allowing us to access medical records documenting their TBI.

After completing the baseline battery, we will give participants an Actigraph. They will wear the Actigraph for 72 hours before starting the intervention. They will also complete a sleep diary on which they will record time to bed and time awake. After these three days, they will return to the research center, and we will download their Actigraph data. We will then train participants to use the light box. Consistent with American Academy of Neurology criteria for intervention studies we will then randomly assign subjects to receive either BWL or DRL using a predetermined, random sequence in blocks of randomly determined size between 6 and 10. A staff member of the BIRC who has no contact with the study participants and is not otherwise involved in the project will do the randomization. He or she will provide the research assistant with a case containing the appropriate light box (note that the BWL and DRL light boxes are indistinguishable). Participants will be asked to record their use of the light boxes and their fatigue on a daily basis. A week after treatment begins participants will be called and asked to complete an assessment of treatment credibility and outcome expectancy.

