After one month of light treatment (T2), we will re-administer the baseline battery along with satisfaction and user experience questionnaires and 3 more days of Actigraphy. One month after T2, we will administer the assessment battery a third and final time (T3). Research team members who conduct outcome assessments will be blind to participants' treatment allocations. They will enter the data only after the participants have completed all study assessments (i.e. after T3) to avoid bias. Participants will be asked not to reveal treatment allocation to research team members. Participants will also be asked to refrain from light treatment in the month intervening between T2 and T3. Upon completion of follow-up, interested participants will be offered a discount coupon to purchase their own light box if they wish to do so.

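### Severe or unanticipated side effects end study participation, not only light treatment, so a participant withdrawn before T2 gives H1 no post-baseline GFI; the bias is probably small and the remedy cheap

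*Combined protocol and SAP*

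**What the plan says.** The rule appears under Study Monitoring and Safety, in section g (the data and safety monitoring plan), in section h (Withdrawal of Subjects) and in section 8 (Research Related Harm/Injury). Section h reads: "subjects will be withdrawn from the study if they experience any clinically significant side effects beyond those anticipated or if side effects are severe". The other three use the same words.

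In three of the four places (all but section h), a milder step comes first: for significant adverse effects, "the participant will be directed to discontinue treatment temporarily and consult their physician". The protocol thus already distinguishes pausing treatment from leaving the study.

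On assessments, Enrollment and Assessments says: "After one month of light treatment (T2), we will re-administer the baseline battery". Study Timelines says: "T3 will take place 4 weeks after light box treatment is completed". Neither says what happens to someone who stops early. Between T1 and T2 there is a daily log: "Participants will be asked to record their use of the light boxes and their fatigue on a daily basis". It is not described as GFI, and the analysis section gives it no role.

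Sections 6.b and 6.c of the analysis plan make GFI the outcome for H1 and analyse everyone randomised by full maximum likelihood. T3 enters only in the maintenance analysis (H3 there, H2 under Objectives). Dropouts and completers are compared on baseline variables. No sensitivity analysis for missing outcomes is described.

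**The concern.** T2 is the only post-baseline GFI in the H1 analysis. A participant withdrawn during the four weeks of light treatment stays in the model through the baseline value alone. Maximum likelihood in effect gives that person the T2 expected of others in the same arm with the same baseline. This is right only if, given arm and baseline, withdrawal is unrelated to the T2 that would have been seen. That assumption is least secure when the loss is caused by a bad reaction to treatment, and comparing baseline values cannot check it.

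The loss may also differ by arm, because the Background describes DRL as relatively inactive biologically. If side-effect withdrawals fall mainly on BWL and those people do worse than predicted, H1 is biased in favour of BWL. A GFI not collected at T2 cannot be obtained later. Withdrawal after T2 loses only T3 and leaves H1 untouched.

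**Working it through.** **1. The plan's own figures reproduce.**
- Enrolment: 80/0.85 = 94.1, so 95. Screening: 95/0.70 = 135.7, so 136.
- Power with N = 80 (noncentral F, 1 and 78 df, noncentrality 80f²): f = 0.37 gives 90.5% (stated 90%), and f = 0.32 gives 80.7% (stated 81%).
- The effect sizes therefore behave as Cohen's f. Read as Cohen's d they would give only about 38% and 30% power. The interaction effect used below is d = 2 × 0.32 = 0.64.

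**2. Inputs the documents do not give (assumptions).** The withdrawal rate w in BWL is taken as 2%, 5% or 10%, which is about 1, 2 or 5 of 47; DRL is taken as 0%. The shortfall δ is how much worse, in SD, the withdrawn would be at T2 than the model predicts.

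**3. Bias in H1.** In general, bias = w(BWL) × δ(BWL) − w(DRL) × δ(DRL). With loss in BWL only, it is w × δ:

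| Assumed T2 state of the withdrawn | δ | w = 2% | w = 5% | w = 10% |
|---|---|---|---|---|
| 0.5 SD worse than predicted | 0.50 | 0.010 | 0.025 | 0.050 |
| At the DRL mean (benefit lost) | 0.64 | 0.013 | 0.032 | 0.064 |
| 1 SD below the DRL mean | 1.64 | 0.033 | 0.082 | 0.164 |

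As a share of d = 0.64, the rows run from 1.6% to 7.8%, from 2% to 10%, and from 5.1% to 25.6%.

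**4. Two-sided type I error.** With SE = √(2/40) = 0.224 and bias b, the error is Φ(b/SE − 1.96) + Φ(−b/SE − 1.96). With no true effect among those who stay:
- δ = 0.5: 5.02%, 5.14% and 5.57% at w = 2%, 5% and 10%.
- δ = 1: 5.09%, 5.57% and 7.32%.

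**5. Direction is not fixed.** If δ = 0.5 in both arms and loss for any reason is 20% BWL against 10% DRL, bias is 0.10 − 0.05 = +0.05 SD. Reversed, it is −0.05 SD. At 15% in each arm it is 0.

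**6. Tipping point.** With an observed d = 0.64 and no shift in DRL, significance is lost when δ exceeds (0.64 − 1.96 × 0.224)/w. That is 1.34 SD at w = 15% and 2.0 SD at w = 10%.

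**7. What the pilot can exclude.** No side effects were reported among 13 randomised participants. The one-sided 95% upper limit is 1 − 0.05^(1/13) = 20.6%, arms pooled, for any reported side effect. The withdrawal rule covers only a subset of these.

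**The case against.** The strongest reply is that the point is immaterial. The protocol calls side effects infrequent, and neither the pilot nor the cited breast cancer trial of 39 women reported any in either arm. At 2% about one BWL participant is lost, and the bias is 0.010 to 0.033 SD. This largely stands, and it is why the point is only a suggested improvement. It does not close the matter: the pilot is too small to exclude higher rates, and small depends on δ as well as on w.

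A second reply is that this is silence rather than a rule. The consent pages are not available, the form allows reference to other source documents, and nothing bars a later assessment. A reader might infer that the plan forbids follow-up after withdrawal; the documents do not say so. What they do say, four times, is that such participants leave the study, and no visible text requires T2 or T3 afterwards.

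A third reply is that the plan already handles dropout through the 15% attrition allowance, maximum likelihood on all randomised subjects and the dropout comparison. The allowance protects numbers, not against bias. Maximum likelihood is a sound primary method, but here it rests on the untested assumption.

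The daily fatigue log might seem to fill the gap. It can do so only if worsening shows before withdrawal; if fatigue worsens after the light stops, the log holds no sign of it. No reduction in bias is claimed for it here.

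**Conclusion.** The concern holds in a limited form. Followed as written, the rule leaves H1 without a post-baseline GFI for anyone withdrawn before T2 because of side effects, and the primary analysis then rests on missing at random for that loss. The likely size is about 0.01 to 0.03 SD, for 2% to 5% withdrawn from BWL only and 0.5 to 0.64 SD worse than predicted. It reaches about 0.08 SD at 5%, or 0.16 SD at 10%, only if those withdrawn end 1 SD below the DRL mean. Rate, arm imbalance, shortfall and direction are all assumptions.

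A reader might infer that the intent-to-treat claim is invalid or that H1 will be materially biased towards BWL. The documents support neither. All randomised subjects remain in the model, the stated power is unaffected, and overturning H1 would need about 1.3 SD worse outcomes in 15% of BWL with no shift in DRL.

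**What to change.** Leave the clinical criteria for stopping light treatment exactly as they are. Then:

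- In all four places, and in the consent wording if needed, separate stopping light treatment from ending data collection.
- Seek T2 and T3 from participants who stop, at the scheduled times (about 4 and 8 weeks after light treatment starts), unless consent to data collection is withdrawn. State this timing explicitly, because Study Timelines ties T3 to completed treatment. Section f already covers remote visits.
- Analyse as randomised and record the reason for every loss by arm.
- Add one delta-adjusted sensitivity analysis of H1 for missing T2. Vary delta separately by arm and extend it until the tipping point is reached. A range ending at 0.64 SD would be too short, given the 1.34 SD above.

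**Cost.** A short edit repeated four times, one extra analysis, and two $20 assessments plus staff contact time per retained participant. For 0 to 5 side-effect withdrawals, payments are $0 to $200. If all 14 to 15 expected losses were assessed (0.15 × 95 = 14.25; 95 − 80 = 15), they would be $560 to $600.

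**Downside.** Off-treatment data may slightly reduce the estimated effect. If those withdrawn end at the DRL mean, 0.64 becomes 0.627 at 2% and 0.608 at 5%. Power with the recovered participants included is then about 79.6% and 77.6%, against 80.7%.
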